4.2.5.2 Sensitivity/supplementary analyses

A sensitivity analysis under the primary estimand will be conducted with missing data imputed based on different withdrawal reasons. This model assumes that some pre-specified subset of patients who withdraw from the study have correlations with future unobserved visits similar to patients in the placebo arm.

- ANCOVA under primary estimand with WP/WOCF imputation after surgery and/or SCS use for CRSwNP and dropout reason based multiple imputation for non-rescued study discontinuation to test the MAR assumption (Section 8.3).

Additional supplementary analyses will be conducted with a different handling strategy for surgery and/or SCS use for CRSwNP.

- ANCOVA with composite strategy for surgery for CRSwNP only, treatment policy strategy for other intercurrent events, and multiple imputation for missing data (including those after rescue SCS use) assuming MAR (Appendix 8.2).
- ANCOVA for repeated measures (without imputation) with while-on-treatment strategy for all intercurrent events, where outcomes after treatment discontinuation, surgery for CRSwNP, or SCS use for CRSwNP will be set to missing (Appendix 8.4 effectiveness estimand).
- ANCOVA for repeated measures (without imputation) with treatment policy strategy for all intercurrent events, where all data as observed through Week 56 will be included

regardless of treatment discontinuation, surgery for CRSwNP, or SCS use for CRSwNP (Appendix 8.5 treatment policy estimand).

4.2.5.3 Subgroup analyses

To explore the uniformity of the detected overall treatment effect, subgroup analyses will be performed for the co-primary endpoints, i.e. change from baseline in total NPS and in bi-weekly mean NBS, and for the key secondary endpoints, bi-weekly mean DSS, LMS and SNOT-22 total score, using an ANCOVA at Week 56 for the following subgroup factors:

- Gender (male vs female)
- Age (18 - 65 vs ≥ 65 years)
- Geographical Region
 - North America includes the US
 - Europe includes Belgium, Bulgaria, France, Hungary, Italy, Poland, Russia, Turkey
 - Asia includes China mainland, Taiwan, Japan, Thailand, Vietnam
 - Rest of the World includes Argentina, Australia, Chile
- CCI [REDACTED]
- Prior surgery for CRSwNP (yes vs no)
- Number of prior surgery for CRSwNP (0, 1, 2 or more)
- Prior SCS use (yes vs no)
- Baseline AERD (yes vs no)
- CCI [REDACTED]
- Atopic status by atopic medical history (yes vs no)
- CCI [REDACTED]
- Quartiles of baseline blood eosinophil (EOS) counts

The quartile of baseline blood EOS counts CCI [REDACTED] will be calculated using the respective measurements at baseline from all the patients in the PFAS, regardless of treatment groups.

For each of the subgroup factors in turn, a separate ANCOVA model will be fitted using the same model terms as used for the primary analysis (defined in Section 4.2.5.1) and for the key secondary endpoints (defined in Sections 4.2.6.1, 4.2.6.2, and 4.2.6.3), including WP/WOCF and MI components, with additional terms for the subgroup main effect and the treatment \times subgroup interaction.

Similar outputs will be presented for each subgroup as for the primary analysis. The p-value for the interaction term will be presented in the summary tables.

In addition, subgroup analyses will also be conducted at Week 56 by cumulative subgroups of EOS counts at baseline (≥ 150 cells/ μL , ≥ 200 cells/ μL , ..., ≥ 500 cells/ μL) and the other direction (< 150 cells/ μL , < 200 cells/ μL , ..., < 500 cells/ μL). For these subgroup analyses, data will be analysed using the ANCOVA model as mentioned in Section 4.2.5.1 and Sections 4.2.6.1, 4.2.6.2, and 4.2.6.3 in each subgroup category.

If there is strong evidence for a differential treatment effect for NPS and/or NBS across subgroups, additional analyses based on the NPS and/or NBS responder analysis may be conducted. Additional terms for the subgroup main effect and treatment \times subgroup interaction will be included in the logistic regression model defined in Section 4.2.5.4.

Subgroup analyses based on PK will also be performed for the change from baseline at Week 56 for co-primary and key secondary endpoints. All patients with at least one post-baseline PK sample collected will be included in this analysis. Patients on Benra will have their median PK concentration calculated based on all observed trough concentrations at steady state during the 56-week analysis period. Values collected after treatment discontinuation or without IP dosing at the previous visit will not be used to derive the median. Patients on Benra will then be grouped to PK quartiles based on their median concentration values and compared against the overall placebo group. A similar ANCOVA model, as described in Section 4.2.5.1 and Section 4.2.6.1 to Section 4.2.6.3, will be used with treatment group (i.e. Benra vs placebo) replaced by a 5-category PK variable (4 PK quartiles for benralizumab and 1 for placebo). Estimates of the treatment effects will be reported based on contrasts between each Benra quartile and placebo.

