4.3. Justification for dose

The benralizumab dose and regimen proposed in the CRSwNP Phase 3 pivotal study will be consistent with the asthma dosing regimen, i.e. 30 mg by SC injection every 4 weeks for the first 3 doses and then every 8 weeks thereafter. This proposal is based on consideration of mechanism of disease (similarity of the inflammatory profile between asthma and CRSwNP, see Section 2.2 Background), and all available safety, efficacy, and immunogenicity data from completed asthma trials, as well as population exposure-response modelling, and stochastic trial simulations from earlier phase benralizumab trials.

Both empirical and population-based analyses of asthma exacerbation rate (AER) data in Phase 2b and Phase 3 asthma patients confirmed 30 mg every 8 weeks (i.e. benralizumab 30 mg by SC injection every 4 week for the first 3 doses, and then every 8 weeks thereafter) as the optimal dose for efficacy, based on annualized AER. The efficacy plateau for pre-bronchodilator forced expiratory volume in 1 second (FEV1) was reached with benralizumab 30 mg every 8 weeks. This regimen demonstrated statistically significant reductions in the AERs, and statistically significant improvements in pulmonary function (FEV1) and total asthma symptom score. Compared with the 30 mg every 4 weeks regimen, the benralizumab 30 mg every 8 weeks regimen was more consistent across studies and endpoints, and no additional benefit was observed by dosing with benralizumab more frequently. Neither body weight nor ADA was found to impact the annualized AER or pre-bronchodilator FEV1.

In the Phase 3 asthma pivotal studies, approximately 20% of patients had CRSwNP in addition to severe asthma. Importantly, the patients with CRSwNP had similar pharmacokinetics (PK) exposure and eosinophil depletion to patients without CRSwNP.

In conclusion, the 30 mg every 8 weeks dosing regimen (including an additional dose at Week 4) is recommended to be used in the benralizumab CRSwNP Phase 3 program. No dose adjustment for CRSwNP is warranted based on the similarity of the inflammatory profile between asthma and CRSwNP, and considerations of PK variability, blood eosinophil count depletion, immunogenicity, exposure-response analysis of efficacy endpoints in patients with severe asthma, and the clinical safety profile of benralizumab.

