8.2.5. Other safety assessments

8.2.5.1. Weight and height

Weight and height will be measured in accordance with schedules provided in the SoA.

The patient's weight will be recorded in kilograms; height will be recorded in centimetres. Weight and height measurements will be performed in light clothing and with shoes off.

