4. ANALYSIS METHODS

4.1 General principles

The primary database lock will occur after all randomised patients have been followed up for the 56-week double-blind treatment period. The final database lock will occur after the last patient completes the OLE.

Analyses at the primary DBL will include all data captured during the double-blind treatment period and selected safety endpoints during the OLE period. Unblinding and data analysis will occur after the primary database lock. Efficacy endpoints will be analysed using the PFAS according to their randomised treatment. Efficacy data collected from patients without comorbid asthma will be listed only. Safety endpoints will be analysed using the Safety Analysis Set (or the OLE set if specified) regardless of comorbid asthma status according to their actual treatment received.

In the primary analysis of co-primary endpoints (and key secondary endpoints unless otherwise stated), an ANCOVA model will be used with treatment arm, baseline score (for the respective endpoint), region, CCI [REDACTED] as covariates. Handling strategy of intercurrent events are specified as follows:

- *Nasal polyp surgery*: a nasal polyp surgery is considered as treatment failure. The composite strategy will be applied where the worst possible (WP) score for the respective endpoint will be used for post-surgery assessments.
- *SCS use for CRSwNP*: SCS use for CRSwNP is considered as treatment failure but less severe than surgery. The composite strategy will be applied where the worst observation prior to the SCS use will be carried forward (WOCF) for post-SCS assessments.
- *Treatment discontinuation*: the treatment policy strategy will be applied.

The analysis includes all the data collected during the study including data collected after discontinuation of study treatment except data collected after surgery and/or SCS use for CRSwNP. For participants who discontinue the study without any rescue event (i.e. NP surgery and/or SCS use for CRSwNP), a multiple imputation (MI) approach will be used to impute missing values assuming missing at random (MAR). The estimates of the treatment effects will be based on contrasts from the ANCOVA model.

Details regarding the estimand for primary and key secondary objectives are provided in [Table 11](#), with additional details including supplementary and sensitivity analyses provided in [Appendix 8.2 to 8.5](#) and [Appendix 8.10](#).

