4.2.2 Demographics and baseline characteristics

The demographics and key subject baseline variables (Section 3.2) will be descriptively summarised based on FAS and PFAS. This summary will be repeated for the OLE period using the OLE analysis set.

CRSwNP and respiratory disease characteristics (Section 3.2) and asthma disease characteristics (Section 3.2) at baseline will be descriptively summarised based on PFAS.

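### PK-quartile contrasts with placebo are non-randomised, yet the SAP calls them treatment effects and its visible model terms include no baseline predictor of exposure such as body weight

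*SAP*

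**What the plan says.** SAP 4.2.5.3 plans a PK subgroup analysis of the Week 56 change from baseline for the co-primary and key secondary endpoints. On the grouping it says: "Patients on Benra will then be grouped to PK quartiles based on their median concentration values and compared against the overall placebo group". The model is described as similar to the one used for each endpoint's main analysis, with the two-level treatment term replaced by a five-level variable (four benralizumab quartiles and placebo). The output is described as follows: "Estimates of the treatment effects will be reported based on contrasts between each Benra quartile and placebo". No caveat about the non-randomised nature of these contrasts is given.

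The covariates come from the main model. SAP 4.1 says "an ANCOVA model will be used with treatment arm, baseline score (for the respective endpoint), region", followed by one redacted term. No covariate is added for the PK analysis. The SAP does limit confounding by adherence: "Values collected after treatment discontinuation or without IP dosing at the previous visit will not be used to derive the median".

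On weight, Protocol 8.2.5.1 says "Weight and height will be measured in accordance with schedules provided in the SoA", and Protocol Table 1 places this at Visit 1. SAP 3.2 lists weight as a baseline variable. Its stated use is in SAP 4.2.2: "The demographics and key subject baseline variables (Section 3.2) will be descriptively summarised based on FAS and PFAS". It is neither a visible covariate nor a visible subgroup factor. Every benralizumab patient receives 30 mg whatever their weight, and the current eligibility criteria set no weight limit. The dose justification in Protocol 4.3 says of the asthma trials: "Neither body weight nor ADA was found to impact the annualized AER or pre-bronchodilator FEV1".

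**The concern.** Randomisation balances the benralizumab arm against the placebo arm. It does not balance a quarter of the benralizumab arm, chosen by each patient's own drug concentration, against all of placebo. Any baseline characteristic that influences concentration will differ between a quartile and placebo. If that characteristic also influences outcome, the contrast mixes its effect with that of the drug.

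Weight is the obvious candidate under a flat dose. If heavier patients have lower troughs, the lowest quartile is heavier than placebo and the highest is lighter. If heavier patients also improve less, the drug looks weaker at low exposure and stronger at high exposure even when its effect is constant. If heavier patients improve more, the distortion runs the other way and could hide a real gradient. The statement in Protocol 4.3 concerns exacerbation rate and FEV1. It does not cover NPS, NBS, DSS, LMS or SNOT-22.

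What is at stake is the reading of an exposure-response display for the five multiplicity-protected endpoints. Presented as treatment effects, the four contrasts could be read as causal estimates by exposure level.

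**Working it through.** **The plan's own figures.** The inputs from Protocol 9.2 and SAP 1.4 are 250 patients randomised 1:1 (125 per arm), SD 2 for NPS and 1 for NBS, differences of 0.85 and 0.4, and two-sided alpha of 0.05.
- Power is 0.919 for NPS and 0.885 for NBS. Their product, treating the endpoints as independent, is 0.81, consistent with the stated overall 80%.
- The smallest significant differences are 1.96 × 2 × √(2/125) = 0.496 and 1.96 × 1 × √(2/125) = 0.248, matching the stated 0.50 and 0.25.

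The documents give no figure for the PK-quartile analysis.

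**Precision of a quartile contrast.** If all 125 benralizumab patients are evaluable, each quartile holds 31.25 on average.
- SE for NPS = 2 × √(1/31.25 + 1/125) = 2 × 0.20 = 0.40. For NBS it is 0.20.
- Power per quartile at the design effects is about 57% (NPS) and 52% (NBS).

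**Bias formula.** Let ρ be the correlation of weight with concentration and r the correlation of weight with outcome change, both as they remain after region and baseline score. The bias of a quartile-versus-placebo contrast is ρ × r × SD × m, where m is the standard normal quartile mean: -1.271, -0.325, 0.325, 1.271. The documents give neither ρ nor r, so both are assumptions.

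| ρ | r | Outer-quartile shift, NPS | Shift ÷ SE |
|---|---|---|---|
| 0, any r | or r = 0, any ρ | 0 | 0 |
| -0.4 | 0.05 | 0.4 × 0.05 × 2 × 1.271 = 0.05 | 0.13 |
| -0.5 | 0.10 | 0.5 × 0.10 × 2 × 1.271 = 0.13 | 0.32 |
| -0.6 | 0.20 | 0.6 × 0.20 × 2 × 1.271 = 0.31 | 0.76 |

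The middle quartiles shift by about a quarter as much (0.325/1.271). In the central row this is 0.5 × 0.10 × 2 × 0.325 = 0.03. NBS shifts are half the NPS values, as is the NBS standard error.

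**Simulation check.** There were 4,000 trials per scenario, with 125 patients per arm and a constant true NPS effect of -0.85.

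| ρ, r | Weight in model | Lowest quartile | Highest quartile | False highest-vs-lowest findings |
|---|---|---|---|---|
| 0, 0.3 | no | -0.85 | -0.85 | 5.3% |
| -0.5, 0 | no | -0.86 | -0.85 | 4.9% |
| -0.5, 0.1 | no | -0.72 | -0.98 | 8.1% |
| -0.5, 0.1 | yes | -0.85 | -0.85 | 5.1% |
| -0.5, 0.2 | no | -0.60 | -1.09 | 16.0% |
| -0.5, 0.2 | yes | -0.85 | -0.85 | 5.4% |

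The simulated shifts agree with the formula. Adjustment restores flat contrasts here because weight is the only confounder in the simulation and acts linearly. The simulation contains no region term.

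**The case against.** The strongest reply is that both links in the chain are assumed. The documents do not say that weight affects benralizumab concentration or that it predicts any nasal outcome. Their one finding on weight is negative, though for other endpoints. Region is in the model and the trial spans four geographical regions, so part of any weight difference may already be absorbed. In the central case the shift is about a third of a standard error. This stands, and it limits how much can be claimed about size.

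Other safeguards exist. Troughs taken after discontinuation or a missed dose are dropped. SAP 8.7 examines ADA against concentrations and efficacy. A population PK analysis will be reported separately, with content not visible here. One model term is redacted, so the absence of weight can be confirmed only for the visible terms. Protocol 6.3.1 and 9.4.1.2 describe the redacted term as a baseline status used for stratification, so it is unlikely to be weight.

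The remedy is also partial. ADA status, disease severity or other correlates of exposure could still confound the contrasts after weight is added. This too stands, and it is why relabelling is needed as well as the covariate.

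None of these replies makes the quartile contrasts randomised or supports calling them treatment effects.

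**Conclusion.** The point holds as a minor one. The contrasts are non-randomised, they are labelled treatment effects, and no visible model term is a baseline predictor of exposure such as weight. Under assumed correlations of -0.4 to -0.6 (weight with trough) and 0.05 to 0.20 (weight with NPS change), with SD 2, an outer-quartile contrast would be off by about 0.05 to 0.3 NPS points against a standard error of about 0.40. The bias is zero if either correlation is zero.

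Three stronger readings are tempting, and the documents do not support them.
- A reader might infer that any prognostic effect of weight must appear as a false exposure-response. It would do so only if weight were also related to trough concentration after the existing adjustments, which the documents do not state.
- A reader might set the lowest-minus-highest gap (twice the shift, about 0.1 to 0.6 points) against the 0.85 design effect. The SAP reports each quartile against placebo, not that gap, and the gap's own standard error is 2 × √(2/31.25) = 0.51.
- A reader might infer that this analysis decides whether the fixed dose is adequate. SAP 4.2.5.3 gives its subgroup analyses the purpose of exploring uniformity of effect, and Protocol 9.4.1.3 calls subgroup analyses exploratory.

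The PK contrasts lie outside the multiplicity scheme, so the primary and key secondary conclusions are unaffected.

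**What to change.** In SAP 4.2.5.3, add baseline body weight as a continuous covariate to the PK-quartile ANCOVA, applied to benralizumab and placebo patients alike. At a minimum, run this as a sensitivity analysis beside the planned model so that the two sets of contrasts can be compared.

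Replace the description of the output as treatment effects. Call the results non-randomised exposure-response associations, and state that they may remain confounded by other factors such as ADA status or disease severity, with or without the weight term.

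The cost is one degree of freedom in an exploratory model and one extra set of outputs. Weight is already collected, so no new data are needed.

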4.2.5.4 Supportive analyses: responder analyses

Patients with missing or non-evaluable observation at the timepoint of interest will be counted as non-responders for in the analysis. Patients who have had surgery or SCS use for CRSwNP by the timepoint of interest will be considered as non-responders.

The proportion of NPS responders with improvement by at least 1 score (defined as change from baseline in total NPS ≤ -1) at Week 24 and Week 56 will be analysed using a logistic regression model with treatment arm, baseline total NPS score, region, CCI, CCI as covariates. Results of the analyses will be presented using odds ratio, together with associated 95% CI and 2-sided p-value.

Cumulative distribution function of absolute changes from baseline in NPS at Week 24 and at Week 56 will be plotted in a figure.

Similar responder analyses will be conducted for NBS responders (defined as change from baseline in NBS ≤ -1) at Week 24 and Week 56. Cumulative distribution function of absolute changes from baseline in NBS at Week 24 and at Week 56 will also be plotted in a figure.

4.2.6 Key secondary efficacy variable

Key secondary efficacy endpoints will be collected during the double blinded period according to the SoA Table 2 in the CSP. No data from the OLE period will be collected for key secondary endpoints. Therefore following analyses specified in Section 4.2.6.1 to 4.2.6.3 only apply to the double blind period at the primary DBL.

4.2.6.1 Difficulty with sense of smell (DSS) score

The change from baseline in bi-weekly mean DSS score will be analysed using a similar ANCOVA as the primary endpoints described in Section 4.2.5.1. DSS scores and the change from baseline will be summarised using descriptive statistics.

The cumulative distribution function of absolute changes from baseline in bi-weekly mean DSS at Week 24 and Week 56 will also be plotted in figures.

Subgroup analyses as mentioned in Section 4.2.5.3 will also be conducted for the change from baseline in bi-weekly mean DSS, including the subgroup analysis by PK exposure quartile.

4.2.6.2 Sinus CT: LMS

The total LMS score and the change from baseline will be summarised by treatment group and by time point using descriptive statistics for all patients in the PFAS. The change from baseline in total LMS will be analysed using ANCOVA model as the co-primary endpoints described in Section 4.2.5.1 but a different intercurrent event strategy (treatment policy) to handle rescue SCS use for CRSwNP. The analyses will use the data collected during the DB period, regardless of whether patients remained on treatment or not. In order to limit the radiation exposure, there is only a single CT scan post-baseline that occurs at Week 56 (or IPD or prior to surgery for CRSwNP), and hence the composite (WOCF) strategy used after SCS use for CRSwNP in the primary estimand is considered less appropriate as for co-primary endpoints. Instead, the analysis will use data collected after SCS use for CRSwNP. A composite strategy will be used for surgery for CRSwNP. If a patient has surgery for CRSwNP before EoDB, the data will be censored after the time of the first surgery for CRSwNP and the worst possible value will be imputed in its place. See Table 13 for a full list of WP values. The Multiple Imputation components described in Section 4.2.5.1 will not be necessary for analysis of LMS scores.

A supplementary analysis of LMS scores will be conducted in which the composite (WOCF) strategy is used for SCS use for CRSwNP. Patients who receive SCS for CRSwNP prior to EoDB/IPD CT scan will have the worst observed score (or baseline score if no post-baseline score available) imputed in place of the observed or missing values. Patients who have surgery for CRSwNP prior to EoDB/IPD CT scan will have the worst possible value imputed whether or not they also receive SCS for CRSwNP. An additional supplementary analysis of LMS scores will be conducted in which patients who have surgery for CRSwNP prior to EoDB/IPD CT scan will have the last observed score prior to surgery for CRSwNP imputed over data collected post-surgery.

Subgroup analyses as mentioned in Section 4.2.5.3 will also be conducted for the change from baseline in LMS, including the subgroup analysis by PK exposure quartile.

